## 7.3 Clinical Laboratory Assessments

Clinical laboratory tests in chemistry, hematology and urinalysis will be performed throughout the study according to the schedule of assessments. The laboratory will also provide eGFR, calculated using the CKD-EPI formula. Descriptive statistics for actual values and change from Baseline values for laboratory tests will be presented for each scheduled measurement. The number and percentage of subjects with values beyond the laboratory normal ranges will be summarized by frequency tables and shift tables. A by-subject listing, including flags for abnormal or out-of-range values, will be provided. The laboratory tests to be performed are listed in Table 5.

Serum Chemistry Panel	Units	Hematology and Coagulation	Units
Albumin	g/L	Hemoglobin	g/L
Total protein	g/L	Hematocrit	%
Alkaline phosphatase	U/L	Red blood cell count	x10^12/L
ALT	U/L	White blood cell count	x10^9/L
AST	U/L	MCV	fL
Bicarbonate	mmol/L	МСН	pg
Bilirubin, total	umol/L	МСНС	g/L
Bilirubin, direct	umol/L	RDW	%
Blood urea nitrogen	mmol/L	Platelet count	x10^9/L
Calcium	mmol/L	MPV	fL
Chloride	mmol/L	Basophils	%
Creatinine	umol/L	Eosinophils	%
Creatinine clearance	mL/s	Lymphocytes	%
FSH	U/L	Monocytes	%
GGT	U/L	Neutrophils	%
Glucose	mmol/L		
Lactate dehydrogenase	U/L	Urinalysis	Units
Cholesterol	mmol/L	Protein	n/a
HDL	mmol/L	Glucose	n/a
LDL	mmol/L	Ketones	n/a
Triglycerides	mmol/L	Bilirubin	n/a
Phosphorus	mmol/L	рН	n/a
Potassium	mmol/L	Nitrites	n/a
Sodium	mmol/L	Specific gravity	n/a
TSH	mU/L	Urobilinogen	n/a
Free T4	mmol/L	Leukocyte Esterase	n/a
eGFR	mL/min/1.73m^2	Microscopic Urine	Units
		Bacteria	n/a
		RBC	n/a
		WBC	n/a
		Epithelial cells	n/a
		Casts	n/a
		Crystals	n/a

Table 5

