- i. Orthostatic hypotension at Screening (Visit 1) or Baseline (Visit 2), defined as a decrease of more than 20 mmHg in systolic BP or 10 mmHg in diastolic BP, or both, following a change from a supine position to a standing position (measured within 1 to 3 minutes of standing); or orthostatic intolerance (e.g., developing symptoms upon standing).
 - NOTE: If the first measurement of a subject's change in BP exceeds the allowable decrease, a second recording is allowed after an additional approximately 5-minute supine rest.
- j. Any clinically significant abnormal electrocardiogram (ECG) finding (e.g., atrial fibrillation) at Screening (Visit 1) or Baseline (Visit 2), as determined by the Investigator or study site designated physician or, if needed, in consultation with a cardiologist
- k. Resting QT interval corrected using Fridericia's formula (QTcF) ≥ 450 msec (male) or ≥ 460 msec (female) at Baseline (Visit 2) or inability to determine QTcF
- 1. Presence of risk factors for Torsades de pointes (TdP), including long QT syndrome, uncontrolled hypokalemia or hypomagnesemia, history of cardiac failure, history of clinically significant/symptomatic bradycardia, family history of idiopathic sudden death or congenital long QT syndrome, or concomitant use of a torsadogenic medication that cannot be discontinued prior to Baseline (Visit 2)
- 27. Have evidence of clinically significant hepatic disorder (e.g., alanine aminotransferase [ALT] or aspartate aminotransferase [AST] >2.0x upper limit of normal [ULN])
- 28. Moderate-to-severe renal impairment, indicated by an estimated glomerular filtration rate (eGFR) of < 50 mL/min/1.73 m² at Screening (Visit 1), based on the Cockroft-Gault formula

MM-120 (LSD) Clinical Study Protocol: MMED008

- 29. Use of any other investigational drugs, devices, therapies or other advanced therapies that, in the opinion of the Investigator, may confound the study results (e.g., stem cell transplantation, gene therapy) within 30 days prior to Screening (Visit 1). Participation in observational trials must be approved by the Sponsor.

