8.2.7. Electrocardiogram

For any visits in which there is an ECG and blood draw, the ECG should be performed prior to the blood draw.

ECG should be performed after 5 minutes of rest in a semi-recumbent position. A qualified designee at the investigative site is responsible for interpreting the ECG, and if needed, in consultation with a cardiologist. If an ECG finding is identified as abnormal and is a clinically significant change from the baseline assessment, then the finding should be entered as an AE and monitored to resolution in accordance with safety procedures described in Section 9.

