10.2.3.2. Other Safety Parameters

Other safety outcomes, including vital signs, ECG parameters and abnormalities, C-SSRS scores, and laboratory parameter values, will be reported by treatment arm. All safety data (scheduled and unscheduled) will be presented in the data listings. Continuous variables will be summarized using descriptive statistics (n, mean, SD, minimum, median, and maximum) by treatment/dose group at relevant timepoints. Categorical variables will be summarized in frequency tables (frequency and proportion) by treatment/dose group at relevant timepoints. Graphical presentations will be used as appropriate.

Where applicable, data will be summarized for the absolute value at each scheduled assessment and for the corresponding change from baseline. For clinical laboratory tests, listings of values for each subject will be presented with abnormal or out-of-range values flagged. The percentage of subjects with values beyond clinically important limits will be summarized by frequency tables and shift tables.

Treatment-emergent ECG abnormalities will be summarized similarly to AEs.

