## 7.5 ECG

Electrocardiogram (ECG) measures will be collected at screening, Baseline and the Day 2 visit. The number and percent of ECG findings of normal; abnormal, not clinically significant; and abnormal, clinically significant will be presented for each scheduled measurement. The following ECG interval measurements will be summarized by presenting descriptive statistics of actual values and change from baseline values at each scheduled visit:

- PR Interval (ms)
- QRS Duration (ms)
- Ventricular Rate (bpm)
- QT Interval (ms)
- RR Interval (ms)
- QTcF Interval (ms)

Listings will include measurements at each scheduled visit as well as any unscheduled visits.

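### SAP 7.3 and 7.5 drop, without saying so, two safety summaries that protocol 10.2.3.2 specifies: laboratory values beyond clinically important limits and treatment-emergent ECG abnormalities

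*SAP*

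**What the plan says.** **Laboratory tests.** Protocol 10.2.3.2: "The percentage of subjects with values beyond clinically important limits will be summarized by frequency tables and shift tables". SAP 7.3: "The number and percentage of subjects with values beyond the laboratory normal ranges will be summarized by frequency tables and shift tables". SAP 7.3 also gives actual values and change from Baseline at each scheduled measurement, and a listing with out-of-range flags. Neither document gives numerical values for the clinically important limits.

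**ECG.** Protocol 10.2.3.2: "Treatment-emergent ECG abnormalities will be summarized similarly to AEs". SAP 7.5: "The number and percent of ECG findings of normal; abnormal, not clinically significant; and abnormal, clinically significant will be presented for each scheduled measurement". It adds actual values and change from baseline for six interval and rate measures, QTcF among them. It plans no ECG shift table and no treatment-emergent count. On timing it says: "Electrocardiogram (ECG) measures will be collected at screening, Baseline and the Day 2 visit". Day 2 is therefore the only scheduled ECG after dosing.

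**Declaration.** SAP section 8 deals with the Week 4 top-line analysis and mentions neither change. Section 1 of the SAP addendum says that it leaves the planned analyses as they were, and its added safety outputs (section 4.1.2) are adverse event tables only.

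**The concern.** The two documents promise different tables. For a reader of the study report, the protocol's summaries answer whether anyone had a marked laboratory change, and whether anyone had an ECG abnormality that was not there before dosing. The SAP's replacements answer weaker questions: how many values lay outside a reference interval, and how many ECGs were called abnormal at each visit.

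Safety and tolerability are a stated objective, and protocol 2.4 says that the safety profile of oral MM-120 in this population is unknown. At stake is whether the report shows the size of laboratory abnormalities and the newness of ECG abnormalities by arm, or leaves both to the listings.

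**Working it through.** The documents state no figure on this point, so the check is mainly a comparison of texts, with one illustration.

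**1. What a normal-range table can show.** Assume the usual low, normal and high categories. Exclusion 27 gives ALT or AST above 2.0 times ULN as its example of an excluded hepatic disorder, so that example does not bar a subject at 1.8 times ULN.

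| Illustrative course | Normal-range shift table | Table on clinically important limits |
|---|---|---|
| normal to 1.01 x ULN | normal to high | not counted, if the limit lies above 1.01 x ULN |
| normal to 5 x ULN | normal to high | counted, if the limit lies between 1.01 and 5 x ULN |
| 1.8 to 5 x ULN | high to high, no shift | counted as a shift, if the limit lies between 1.8 and 5 x ULN |

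The first two rows cannot be told apart in the SAP's table, and the third does not register as a change.

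**2. Background counts.** Inputs: 36 subjects per arm (SAP section 9); four required post-dose laboratory draws, on Day 2 and at Weeks 4, 8 and 12 (Schedule of Activities; Weeks 1 and 2 are optional). Assumption: a fraction p of healthy values lies outside the normal range, with p = 5% and a range of 2% to 10%.

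- Per analyte and visit: 36 x p = 36 x 0.05 = 1.8 subjects per arm (0.7 to 3.6).
- Per analyte, at least once in four draws: 1 - (1 - p)^4 = 1 - 0.95^4 = 18.5%, or 6.7 of 36 (7.8% to 34.4%, or 2.8 to 12.4 of 36). This treats draws as independent. Repeat values in one subject correlate, so it is an overstatement.

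To gauge dilution, suppose that 20% of the subjects without a background flag acquire one from the drug. The active-arm rate is then b + 0.20 x (1 - b), where b is the background rate. Exact Fisher power, 36 against 36, two-sided 0.05:

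| b | Active-arm rate | Power |
|---|---|---|
| 0% | 20.0% | 0.75 |
| 1% | 20.8% | 0.69 |
| 5% | 24.0% | 0.53 |
| 18.5% | 34.8% | 0.26 |

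No such test is planned. The table only measures how far contrast between arms fades as background rises.

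**3. What per-visit ECG counts can show.** Let x subjects in an arm of 36 be abnormal, not clinically significant, at Baseline and y on Day 2, with the same 36 recorded at both. The number newly in that category on Day 2 can lie anywhere from max(0, y - x) to min(y, 36 - x). If x = y and both are at most half the arm, it can be anything from none to all of y. The two counts do not settle it.

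The clinically significant category is different. Exclusion 26j bars subjects with such a finding at Screening or Baseline, so one on Day 2 is new, apart from eligibility deviations.

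**4. Whether adverse event reporting fills the gap.** Protocol 8.2.7 says of an abnormal ECG that is a "clinically significant change from the baseline assessment, then the finding should be entered as an AE". Protocol 8.3.2 does the same for laboratory results that the Investigator judges clinically significant. Protocol 9.1 ties that judgement to the abnormality causing signs or symptoms or needing active intervention. A marked but silent laboratory or QTcF change may therefore never become an adverse event.

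**The case against.** The strongest reply is that little is lost.

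- SAP 7.3 keeps shift tables and change from Baseline. SAP section 4 adds minimum and maximum by treatment group, so an extreme value shows in its arm.
- SAP 7.5 gives change from baseline for QTcF and five other measures, and exclusion 26j makes the most important Day 2 ECG category new by design.
- Findings judged clinically significant reach the treatment-emergent adverse event tables, by severity and by grade 3 or higher.
- Background flags should be similar across randomized arms, and placebo is shown alongside.
- Protocol section 10 calls itself a general description and leaves detail to the SAP. It defines no limits, so a limits table has to be created.

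All of this stands, and it bounds the loss without closing it. A minimum or maximum shows one value, not how many subjects crossed a limit or where they started. Adverse event capture rests on judgement. Leaving detail to the SAP covers choosing the limits; it hardly covers replacing them with another criterion undeclared.

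A reader might go further and infer that background noise swamps any safety signal, or that nothing planned could show a relation to dose. The documents do not support either. Pooling all analytes within a subject would make nearly everyone look flagged, but the SAP plans no such count. Read analyte by analyte and by arm, the background is modest under the 5% assumption, and the change-from-baseline and adverse event tables can show a dose trend.

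**Conclusion.** Both discrepancies are real, and SAP section 8 declares neither. The consequence is moderate: laboratory signals are diluted and their magnitude is hidden, and new ECG abnormalities judged not clinically significant cannot be told from old ones. Under the assumed 5% rate the background is 1.8 of 36 subjects per analyte per visit. The true dilution depends on rates and limits that the documents do not give. Protocol 10.2.3 and SAP section 7 plan no safety inference, so no error rate or planned power is affected. The point is worth acting on because the protocol's own two summaries can be produced from data already collected.

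**What to change.** - **SAP 7.3:** keep the normal-range frequency and shift tables. Add a frequency and shift table on clinically important limits, taken from a source independent of the trial data and fixed before unblinding. The addendum records that the primary endpoint has been reviewed unblinded, so limits added after that should be dated and labelled as such, with their source stated.
- **SAP 7.5:** add a Baseline-to-Day 2 shift table of the three ECG categories, and the number and percent of subjects with a treatment-emergent ECG abnormality by arm. Define treatment-emergent at the level of the finding, so that a new abnormality in a subject already abnormal at Baseline is counted.
- **SAP section 8:** list and justify any remaining departure from protocol 10.2.3.2.

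The cost is a table of limits, the added laboratory and ECG outputs and their programming. No new data are needed, and no planned output is lost.

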## **Clinical Laboratory Parameters with Standard Units**

## 7.4 Vital Signs

Descriptive statistics for actual values and change from Baseline values for vital signs will be presented for each scheduled measurement. Vital sign parameters include:

- height (cm, measured only at baseline)
- weight (kg)
- BMI  $(kg/m^2)$
- systolic and diastolic blood pressure (mmHg)
- heart rate (beats per minute)
- temperature (°C)
- respiratory rate (breaths per minute)
- orthostatic blood pressure (mmHg)
- standing pulse (bmp)

Measurements from unscheduled visits will be excluded from the analyses but will be included in the data listings.

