25	Threshold dose – minimum dose at which psychoactive effects are perceivable by patients on average
50	Dose that is above threshold but unlikely to result in significant "psychedelic effects"
100	Lower of two doses that reliably results in a "psychedelic effect" while minimizing "bad drug effect"
200	Higher of two doses that reliably results in a "psychedelic effect"

Thus, the 4 doses of MM-120 administered in the current study are expected to have a dose-dependent response. Based on historical data in other patient populations, higher doses are expected to be associated with perceptual alterations including visual and auditory disturbances

[figure not shown]
(including hallucinations), emotional volatility and a dose-dependent autonomic stimulation (transient tachycardia, hypertension and pupillary dilation). The autonomic effects of LSD are typically mild and transient and rarely require intervention. The Sponsor concluded that no further dose increase beyond 200 µg (freebase-equivalent) would be required for predicted changes on HAM-A.

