9. SAFETY CONSIDERATIONS

9.1. Definition of an Adverse Event

An AE is any untoward medical occurrence in a research subject, whether or not considered drug related which occurs during the conduct of a clinical trial. Any change in clinical status that is considered clinically significant by the PI should be documented. AEs occurring prior to randomization should be documented in medical history. AEs occurring after randomization should be documented in the AE log. Adverse events include any clinically significant changes not present prior to drug administration.

An AE includes:

- An unexpected worsening, excluding minor fluctuations, in the nature, severity, frequency, or duration of a pre-existing condition.
- A new condition detected or diagnosed after investigational product administration even though it may have been present prior to the start of the study.
- Injury or accidents: If a medical condition is known to have caused the injury or accident, the medical condition and the accident should be reported as 2 separate medical events (e.g., for a fall secondary to dizziness, both "dizziness" and "fall" should be recorded separately).
- An investigational abnormality (e.g., laboratory parameter, vital sign, ECG) only if the abnormality which occurs during the conduct of a clinical trial. Any change in clinical status, ECGs, routine labs, physical examinations, etc., that is considered clinically significant by the Investigator based on at least one of the following criteria;
 - Induces clinical signs or symptoms
 - Requires active intervention
- Signs, symptoms, or the clinical sequelae of a suspected interaction.
- Signs, symptoms, or the clinical sequelae of a suspected overdose of either investigational product or a concomitant medication.

All observed and subject reported AEs and SAEs will be recorded from time of randomization until the end of study. SAEs will be reported per FDA guidelines.

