## 4 GENERAL CONSIDERATIONS FOR DATA ANALYSIS

Unless otherwise specified, continuous variables will be summarized by presenting the number of non-missing observations, mean, standard deviation, median, 25th and 75th percentiles, minimum, and maximum. Categorical variables will be summarized by presenting the number of subjects and percentage for each category.

Summary results will be provided by treatment group and where appropriate overall for all subjects. All tabulations will be based on pooled data across centers.

Subject data will be listed, sorted by treatment group, investigative center and subject number. When applicable, listings will be sorted by visit and assessment date/time as well.

Analyses will be performed using SAS for Windows statistical software, version 9.4 or higher (SAS, Cary, NC), except where other software may be deemed more appropriate.

CTI Clinical Trial and Consulting Services (Covington, KY) will perform all efficacy and safety statistical analyses.

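### SAP 7.4 summarises dosing-day vital signs only by scheduled timepoint, so no table planned in the SAP shows how many subjects at each dose had a blood pressure or heart rate peak

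*SAP*

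**What the plan says.** SAP 7.4 states: "Descriptive statistics for actual values and change from Baseline values for vital signs will be presented for each scheduled measurement". On other readings it states: "Measurements from unscheduled visits will be excluded from the analyses", while keeping them in the listings. SAP section 4 defines descriptive statistics as n, mean, SD, median and the 25th and 75th "percentiles, minimum, and maximum". SAP 7.4 mentions no per-subject maximum, count beyond a limit, shift table or abnormal flag, and the addendum adds nothing on vital signs.

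The neighbouring sections do plan counts of subjects. Laboratory tests get out-of-range frequencies and shift tables (SAP 7.3). ECG and physical examination get normal/abnormal counts (SAP 7.5 and 7.6).

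The protocol bears on the point in five places:
- Section 2.3 expects, at higher doses, "emotional volatility and a dose-dependent autonomic stimulation", which it spells out as transient tachycardia, hypertension and pupillary dilation. It describes these effects as typically mild and seldom needing intervention.
- Section 8.2.3 schedules nine post-dose readings, at 0.5, 1, 1.5, 2, 4, 6, 8, 10 and 12 hours.
- Section 8 foresees extra procedures when clinically necessary.
- Section 9.1 treats an abnormal vital sign as an adverse event if it is "considered clinically significant by the Investigator based on at least one of the following criteria". The two criteria are that it causes signs or symptoms, or that it needs active intervention.
- Section 10.2.3.2 states: "All safety data (scheduled and unscheduled) will be presented in the data listings". It also promises frequency and shift tables for the share of subjects beyond limits of clinical importance, directly after a sentence on laboratory tests.

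**The concern.** Vital signs are a named safety endpoint (protocol section 3), and SAP 6.1.2 says the final target dose will also weigh safety. For an expected, transient, dose-related effect, the natural question is how many subjects at each dose had a marked rise, and how large each subject's peak was. Subjects may peak at different times, so a timepoint summary does not answer that.

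The adverse event tables fill the gap only in part. A large transient rise with no symptoms and no intervention does not qualify, and the protocol itself expects intervention to be rare. For such rises, the by-dose count would have to be assembled by hand from listings.

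**Working it through.** The plan gives no figure for vital-sign peaks, so there is none to reproduce. The check sets the passages side by side, then asks how far the planned statistics determine a count of subjects.

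**1. Where each kind of dosing-session finding appears**

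| Finding | SAP 7.4 table | AE table | Listing | Subjects counted by arm |
|---|---|---|---|---|
| Scheduled reading, high, with symptoms or intervention | yes, by time | yes, if judged clinically significant | yes | yes, as an AE |
| Scheduled reading, high, neither | yes, by time | no | yes | no |
| Reading at an unscheduled visit, high, neither | no | no | yes | no |
| Extra reading within Visit 3B, high, neither | not stated | no | yes | no |

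**2. One timepoint**

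Input: 36 subjects per arm (SAP section 9). Let L be any reporting limit.
- 0.75 × 36 = 27, so under the usual SAS definition the third quartile is the average of the 27th and 28th ordered values.
- If the third quartile < L ≤ maximum, the 27th value is below L and the 36th is at or above it. The number at or above L is therefore between 1 and 36 − 27 = 9, which is 1/36 = 2.8% to 9/36 = 25%.
- Protocol 10.2.3.2 lists no quartiles. With only the median below L, the upper bound is 36 − 18 = 18.

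**3. Nine timepoints**

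Suppose the same holds at every time.
- Fewest subjects reaching L at least once: 1 (the same subject throughout).
- Most: the smaller of 36 and 9 × 9 = 81, which is 36.

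The reported means and SDs may narrow this in a given data set. They still do not link a subject's readings across times.

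**4. Illustration with an absolute limit**

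These values are assumed, not taken from the documents: mean systolic pressure 118 mmHg, SD 10 or 12, within-subject correlation 0.3 or 0.6, mean rise 10 to 20 mmHg peaking near 3 hours. The limit is 140 mmHg, the protocol's eligibility ceiling.

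| Rise, SD | Highest timepoint mean | Share reaching 140, correlation 0.3 | Share reaching 140, correlation 0.6 |
|---|---|---|---|
| 10, 10 | 127 | 28% | 21% |
| 10, 12 | 127 | 41% | 30% |
| 15, 10 | 132 | 44% | 35% |
| 15, 12 | 132 | 55% | 43% |
| 20, 10 | 136 | 62% | 51% |
| 20, 12 | 136 | 69% | 56% |

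Within a row, the distribution at each single time is identical, so the timepoint tables would be expected to look the same. The share of subjects with a peak still differs by 7 points (28 − 21) to 13 points (69 − 56). It depends on a correlation that no planned table reports. There is no placebo comparator here, and part of each share is reading noise.

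**5. Illustration with staggered rises**

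Also assumed: a 25 mmHg rise starting at one of four readings, reading SD 7 mmHg, nine readings, and a baseline with the same noise.
- Peak of the mean curve: 25 × 1/4 = 6.25 mmHg if the rise lasts one reading, and 25 × 2/4 = 12.5 if it lasts two.
- Simulated mean of each subject's maximum rise: about 25 and 29 mmHg, against 10 on placebo.
- Simulated share rising by at least 25 mmHg: 50% and 67%, against 4%. The 50% largely follows from setting the rise equal to the threshold.
- Statistics already planned, at 36 per arm: the timepoint maximum change averages about 39 to 43 mmHg against 21 on placebo, and the third quartile about 15 to 24.5 against 6.5.

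In this scenario the planned tables would show that something happened. They would not show to how many subjects.

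**The case against.** The strongest reply is that the plan already shows the extremes, and much of it stands.
- A reader might infer that only means are reported. That is wrong: quartiles, minimum and maximum are planned at each scheduled time by arm, and step 5 shows they would carry a signal.
- A reader might infer that no asymptomatic abnormality becomes an adverse event. That is too broad: under protocol 9.1, the need for active intervention is enough on its own. Such events enter the adverse event tables, which are split out for the dosing day (SAP 7.2.6, addendum 4.1.2).
- A reader might infer that peaks are counted nowhere. Those that qualify as adverse events are counted by arm, all readings are listed, and protocol 11.6 provides for monthly review of blinded safety listings.
- A reader might infer that every extra dosing-day reading is excluded. The SAP wording covers unscheduled visits, and Visit 3B is a scheduled visit. The SAP does not say how a repeat reading within it is handled.
- Protocol 10.2.3.2 may already promise limit counts for vital signs.

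There are also fair cautions about the remedy. Heart rate does not decide eligibility at Visit 3A (protocol 8.1.4), so a subject may be dosed with a rate already above a chosen limit. Unscheduled readings also give closely watched subjects more chances of a high value.

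None of this supplies the missing count. A timepoint maximum describes one subject at one time. If protocol 10.2.3.2 does cover vital signs, SAP 7.4 omits an analysis the protocol promised; if it does not, neither document plans one.

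**Conclusion.** The point holds as a gap in reporting. The SAP plans no per-subject post-dose peak and no limit count for vital signs. The number of subjects at each dose with a transient blood pressure or heart rate peak, short of an adverse event, cannot be read from its tables.

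The bounds of 1 to 9 subjects at one time and 1 to 36 over nine times rest only on 36 per arm and on the limit lying between the third quartile and the maximum. They are worst-case bounds. Under the assumptions in step 4, identical timepoint distributions leave the share uncertain by 7 to 13 percentage points. Those illustrations are not evidence about this drug.

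No primary conclusion, power figure or design feature is affected, and no inference on safety is planned. The change is nonetheless worth making, because it is cheap and bears directly on the by-dose safety comparison that the dose choice is meant to weigh.

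**What to change.** In SAP 7.4, keep the timepoint summaries and add, by arm for the dosing session:
- descriptive statistics of each subject's maximum post-dose systolic pressure, diastolic pressure and heart rate, and of the maximum change from Baseline (SAP 4.7 already defines Baseline as the last value before dosing);
- the number and percentage of subjects newly above reporting limits chosen by the sponsor and fixed before unblinding, counted among subjects not above the limit before dosing. These are reporting cut-offs only, not clinical rules.

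Base the main table on the nine scheduled readings. Repeat it with unscheduled and repeat Visit 3B readings included, and state how repeat readings are handled. Reconcile SAP 7.4 with protocol 10.2.3.2 by saying whether its limit counts cover vital signs. The addendum records that the primary endpoint has been reviewed unblinded, so a table added after that point should be labelled ad hoc, with limits taken from a source already fixed.

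The cost is one or two extra tables and no new measurement. The version with unscheduled readings may favour detection in more closely monitored subjects, which is why both versions should be shown.
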